
Longitudinal Care Management

Participants will be followed by the study team for care management for three months. During the initial recruitment interview, the RC will ask the participant about preferences and schedule ongoing times to communicate based on participant preferences. All participants will be contacted by the RC within 3-4 days of enrollment by the preferred method of contact (e.g. text, call) to check-in. Participants who received buprenorphine will receive a phone call within 24 hours by a member of the study team. The RC will

work with the study participant to establish with a new primary care provider, or schedule and attend a follow-up appointment with their existing primary care provider.

Additionally, tailored to each participant, the RC will work to actively connect participants to substance use treatment and community mental health providers. Previously care management tasks included coordinating care with existing providers, providing referral and information for housing, managing care for substance use, meeting participants during subsequent HMC ED or outpatient visits to check-in and accompany participants to HMC appointments as needed.⁹ Care management tasks will be logged and tracked in RedCap by the RC and other members of the study team.

Care Plan

During the initial recruitment, participants will be notified that a Care Plan will be placed in the Emergency Department Information Exchange (EDIE). The Emergency Department Information Exchange (EDIE) system allows team members to implement electronic health care record innovations, such as the creation of care plan notifications that provide the care team contact information for the study team which can be viewed across emergency department sites utilizing the system. EDIE also provides real-time work-flow integrated electronic alerts that allow collaborative team providers to be notified when patients make recurrent visits to an emergency department in the state of Washington and Oregon. Care Plans in EDIE are used as standard of care at HMC and the care plan for ED-LINC was adapted from existing projects (See Appendix B)

Weekly Supervision and Case Conference

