- 4. Coercion:** As described in the informed consent form procedures, patients will be informed that the research is voluntary and non-participation will have no impact on their receipt of routine clinical care. Research team members who have clinical roles at Harborview Medical Center may come in to contact with patients who may be eligible for study participation during the course of their hospital clinical work. However, the

informed consent procedures will only be conducted by research team members who are not actively seeing patients on clinical services in order to avoid potential coercion.

5. **Medication side effects:** Patients may experience study-related psychotropic medication side effects. Although patients may tell a variety of study team members about potential medication side effects (e.g., care manager, follow-up interviewers), only licensed medical doctors will follow-up with psychotropic medication symptom assessments and recommendations. All administrations of medications associated with this study will be provided by licensed medical doctors who evaluate the benefits of the medication greater than the potential risks. The clinical team will assess any medical side effects and document any side effects that they become aware of.

V. DATA AND SAFETY MONITORING PLAN

This Human Subjects Research meets the definition of a clinical trial

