Given the high frequency of AE/SAE events in the study population, and having identified those SAEs/AEs that we anticipate to be study-related in the patient consent form, the study team has opted not to systematically assess for AEs or SAEs at each patient contact. However, the study team may become aware of AEs/SAEs through routine interactions with study subjects. Examples include while scheduling interviews or other patient contact, during baseline or follow-up interviews, intervention related activities, within the EMR, through a public records search (e.g., WA state death records), from public posts or private messages sent through the subject's social media (e.g., Facebook), or relayed by an alternate point of contact for the subject. Study team members will ensure that the PI and other relevant team members (e.g., research coordinator) are made aware of any relevant problems or SAEs via email, phone, or in-person within 24 hours.

SAEs/AEs that the study team becomes aware of through the course of conducting study procedures will be reviewed by the PI and study team to assess relatedness and expectedness will be classified by attribution, or an assessment of the relatedness to participation in the study protocol, with particular regard to the intervention. Specifically, they will be classified as one of the following:

- 1) **Not Related**
- 2) **Probably Related**
- 3) **Related**

AE/SAE and Unanticipated Problems Reporting

Study team members will report unanticipated problems on the Reportable New Information (RNI) form to the IRB, consistent with the UW IRB requirements. The UW IRB definition of Unanticipated Problem includes *a problem or event that meets all of the following criteria: unexpected, probably related to study, and places subjects at greater risk of harm*. Events meeting these criteria must be reported on a Reportable New Information (RNI) form to UW IRB within 10 business days. AEs/SAE's that are not unanticipated problems will not be reported. Additionally, [name] will notify the NIDA Project Officer of any unanticipated problems or significant human subject protection issues within 24 hours of discovery.

Anticipated AE/SAE

Anticipated AEs/SAEs will be tracked systematically and will be reviewed within 24 hours of discovery by the study PI to determine if it is an unanticipated problem. The following AEs/SAEs are anticipated in this study population and will be tracked systematically:

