- Suicidality including fatal suicide and non-fatal suicide attempt
- Overdose (fatal and non-fatal)
- Hospitalization
- Medication side effects

As mentioned above, the study team may become aware of one of these anticipated AEs/SAEs through a variety of means, which may include self-report by the subject while completing baseline or follow-up interviews, intervention related activities, relayed by an alternate point of contact for the subject, within their EMR or EDIE, through a public records search (e.g., WA state death records), or public posts or private messages sent through the subject's social media (e.g., Facebook). Any clinical questions about medications and possible/probable side effects will be triaged to the study PI ([name]) and her mentor, [name] (psychiatrist) to determine if it is related to the study and to make a determination about medication recommendations, reporting, and next steps. Anticipated AEs/SAEs will be systematically tracked using an Excel document to track the event and any comments related to this event. Specific actions around the event will also be documented if necessary. After the study PI is notified a decision will be made to determine if it is an unanticipated problem and this will be documented in the Anticipated AEs/SAEs log. See the Subject Suicidality Safety Protocol (see Appendix C) for details regarding how the study team will address subject suicidality during the conduct of the trial.

Other Patient Safety Reporting

Any other unanticipated problems, compliance issues, or safety concerns identified by the study team will be addressed within the study team including [name] and/or [name], and/or other study team members as appropriate, to assess severity and what steps, if any, are appropriate to take.

Protocol Deviations

The study team may determine the need to deviate from the approved study protocol. The team will make every effort to anticipate the need for protocol deviations and have these approved by the UW IRB prior to engaging in a change to procedures; however, the study team may be required to make deviations to eliminate hazards to patient safety without prior IRB approval.

The study team will document any known instances of non-compliance and report to the IRB per UW Human Subject Division policies per specifications in Table A.

Table A. Protocol Deviation or other Problems Reporting Requirements

Event Type	UW IRB Reporting

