REDCap data quality will be monitored periodically by the study PI and/or data analyst. In the event that any changes need to be made to the data, these changes will be made directly in REDCap. There is a data logging tool in REDCap that allows administrators to track changes to the project. This tool provides access to an audit trail created by REDCap. For each entry that changes data in the database, REDCap records the date, time, username of the person logged in at that time, the type of event and the changes that were made. This audit trail in the data logging tool stores every entry/change throughout the life of the database. Specific checks for completion and accuracy are outlined below for the primary and secondary outcomes and for intervention and usual care activity. Certain patient-reported outcomes (PRO) will be used in the 'Anticipated AE/SAE' log as well. Specifically, PRO's on suicide and overdose will be reviewed as described above.

- Feasibility**

Feasibility measures include enrollment rates, retention rates at each outcome and followup assessment, intervention completion rates and number and types of contacts made by the interventionist. At team meetings, the CONSORT diagram will indicate enrollment and retention rates. At least monthly, the study RA/RC and PI will review the ED-LINC contact log in RedCap for completeness, accuracy and content. Feasibility of implementation will also be assessed using specific assessments of ED-LINC participants at the 6-month follow-up visit. The rates of completion of these assessments will be assessed.

- Substance Use and TLFB**

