If a patient indicates anything greater than 0, “Not at all,” on PHQ-9 item #9, the interviewer will ask a Yes/No follow-up question, labeled #9a *“Over the past two weeks, have you had any plans to harm yourself or take your own life?”* (or “in the past month” for follow-up interviews). If the patient endorsed a “Yes” to item 9a, following completion of the assessment (or earlier if needed), the interviewer will provide the patient with a suicide crisis line and call the study’s 24/7 cell phone after the assessment to inform the study clinical team about the patient. A member of the clinical team will assess the patient either in person at the hospital or via phone to assess risk and safety plan. If there is imminent danger of self-harm the interviewer or member of the study team will inform the participant of the need to inform hospital staff. Of note, if during the baseline interview or during the initial follow-up by the study team to baseline interview responses the study team learns that the subject’s initial injury was due to a suicide attempt, the subject will be withdrawn by the study team per the exclusion criteria. If the study team learns that the initial injury was due to a suicide attempt at any other point during the subject’s trial participation, the subject will be eligible to continue study participation.

If the patient reports a “No” to item 9a, but is otherwise positive on PHQ-9 item #9, the interviewer will provide the patient with a suicide crisis line (see below). A member of the clinical team will visit the patient in the hospital to assess risk and discuss suitable safety planning.

Should the patient inform the interviewer that they have current suicidal ideation and intent outside of the interview questions; the interviewer will inform hospital staff. If the patient

indicates they are having suicidal thoughts at any other time during the baseline assessment, even if the response to the PHQ-9 item 9 is 0, the recruiter will inform the clinical team following completion of the baseline assessment who will, in turn, follow the aforementioned procedures according to randomization assignment.

Suicidality or suicidal behavior discovered at follow-up

The following protocol is initiated if a subject indicates anything greater than 0, “Not at all,” on PHQ-9 item #9.

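### The protocol promises systematic tracking of four anticipated harms but describes a log of events found passively, with no described question on medication side effects or suicide attempts and unequal contact between arms

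*Protocol*

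**What the plan says.** Protocol section V.A makes two statements close together. Under AE and SAE Identification, because such events are frequent in this population, "the study team has opted not to systematically assess for AEs or SAEs at each patient contact". Under Anticipated AE/SAE, it lists suicidality (including fatal suicide and non-fatal attempts), overdose, hospitalization and medication side effects, introduced by "The following AEs/SAEs are anticipated in this study population and will be tracked systematically".

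The same section explains the tracking: "Anticipated AEs/SAEs will be systematically tracked using an Excel document to track the event and any comments related to this event". On how events come to light, it says "the study team may become aware of one of these anticipated AEs/SAEs through a variety of means", naming self-report in interviews, intervention activities, alternate contacts, the EMR, EDIE, public records and social media.

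The sources for each harm are set out elsewhere in the protocol:

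- **Patient-reported items.** Section VII.B.2 says that certain patient-reported outcomes feed the log, and specifies those "on suicide and overdose will be reviewed as described above". Side effects are not named.
- **Side effects.** Section IV.C.5 places the starting of medications, including buprenorphine, among the main study risks. Section IV.D.5 has the clinical team assess side effects and "document any side effects that they become aware of".
- **Suicidality.** Appendix C puts PHQ-9 item 9 (thoughts) in every assessment and adds item 9a only when item 9 is above 0. The baseline subsection words 9a as plans over two weeks, or "in the past month" at follow-up. The follow-up subsection first words it as current thoughts of ending one's life, then repeats the plans wording with a one-month look-back.
- **Records.** Section VII.B.2 has EDIE data pulled for all consented patients.

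Interviews are at 1, 3 and 6 months (section III, Follow-up Interviews).

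**The concern.** Systematic logging and systematic ascertainment are different things. A log can be kept to a high standard and still be nearly empty if nobody is asked. The protocol uses the word for the first, and a reader of the eventual report will probably take it to mean the second.

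Side effects are the clearest case. The effects listed in section IV.C.5 (headache, upset stomach, nervousness, sleep disturbance, dizziness) rarely lead to an ED or hospital visit, so EDIE and the EMR will seldom show them. If they are not elicited, a low count says little about tolerability.

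For suicidality, the listed events include attempts, but the described items do not ask about attempts. Someone who made an untreated attempt between interviews and now scores 0 on item 9 would not reach item 9a.

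The chance of discovery also differs by arm. ED-LINC participants have three months of care management and a study phone (section III.G), and "Participants who received buprenorphine will receive a phone call within 24 hours by a member of the study team". Usual-care activity ends when the patient leaves the ED or hospital (section III, End of Study Participation). More contact means more chances to hear of an event.

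**Working it through.** The plan states no expected count or rate for the log, so there is no figure to reproduce. The check compares each harm with its described source, then does simple arithmetic.

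**1. Harm against described source**

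| Harm | Described active question | Source common to both arms |
|---|---|---|
| Hospitalization | none named as feeding the log | EDIE |
| Overdose | patient-reported item, content and look-back not shown | that item; EDIE if treated |
| Suicide or attempt | items on thoughts and plans; other items on suicide not shown | those items; EDIE, EMR or death records if treated or fatal |
| Medication side effects | none described | none described |

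**2. Time covered by item 9a under the one-month wording**

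Inputs: interviews at months 1, 3 and 6; look-back of one month; about 20% attrition anticipated (section III, Follow-up Interviews).

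- Windows covered: months 0–1, 2–3 and 5–6, which is 1 + 1 + 1 = 3 months.
- Share of follow-up: 3/6 = 50% if every interview is completed.
- At 80% retention: 0.50 × 0.80 = 40% of person-time.
- Not covered: months 1–2 and 3–5.

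These are upper limits for 9a, because it is asked only when item 9 is above 0. Under the current-thoughts wording, the item covers almost none of the interval. No look-back is stated for item 9 itself.

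With a look-back to the previous interview, the windows are 1, 2 and 3 months: 1 + 2 + 3 = 6 of 6 months for someone who completes all three.

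**3. What a zero side-effect count would mean (illustration only)**

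None of these inputs is in the documents. Assume 10 ED-LINC participants start buprenorphine, a proportion p = 0.20 to 0.30 have a side effect, and a proportion v = 0.30 to 0.50 of those volunteer it. Then P(none recorded) = (1 − p·v)^10.

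| | v = 0.30 | v = 0.50 | all asked (v = 1) |
|---|---|---|---|
| p = 0.20 | 0.94^10 = 0.54 | 0.90^10 = 0.35 | 0.80^10 = 0.11 |
| p = 0.30 | 0.91^10 = 0.39 | 0.85^10 = 0.20 | 0.70^10 = 0.03 |

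The last column assumes that everyone is reached and answers. If only 80% are reached at a single contact, and those not reached report nothing, it becomes (1 − 0.20 × 0.80)^10 = 0.84^10 = 0.17 and (1 − 0.30 × 0.80)^10 = 0.76^10 = 0.06. On these assumptions, a zero count under volunteering is quite compatible with a side-effect rate of 20% to 30%. Under direct questioning it is much less so.

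**The case against.** The strongest reply is that the protocol discloses its choice. It says openly that adverse events are not assessed at each contact, gives the reason, and defines tracking as keeping a log, with the investigator reviewing events within 24 hours of discovery. On that reading the wording is loose and nothing more. This stands in part: nothing is concealed. It does not tell a reader how complete the counts will be.

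The other side also blocks several stronger readings that a reader might infer:

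- **That nobody is asked about side effects.** The interview and care-management forms are not in the documents, and neither is the content of the 24-hour call. Section V.A names self-report in interviews as one possible source for all four harms, and section IV.D.5 gives the clinical team a duty to assess side effects. The documents support only that no question or schedule is described.
- **That half of all suicidality is missed.** The 50% concerns one of two conflicting wordings of one gated item. Appendix C is a risk-response procedure and is not presented as the log's data source. The patient-reported items on suicide in section VII.B.2 are not reproduced and could include attempts.
- **That attempts and deaths are shown to be undercounted.** Death records, the EMR and EDIE do not depend on a one-month window. Only untreated attempts are exposed, to an unknown extent.
- **That any shortfall is the same in both arms.** The contact schedules point the other way. The likely direction is more events found in ED-LINC, but its size cannot be computed.
- **That the trial will claim tolerability from these counts.** The SAP has no safety outcome and no between-arm analysis of adverse events. The risk lies in how the counts may later be reported or read.

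**Conclusion.** The concern holds in a limited form. The commitment to systematic tracking is not matched by a described method of systematic ascertainment. The gap is clearest for medication side effects, where no eliciting question, schedule or common source is described. For suicidality, the described items do not ask about attempts, and the two follow-up wordings of item 9a contradict each other and must be reconciled. Coverage by that item is at most 3 of 6 months (40% of person-time at 80% retention) under one wording and close to nothing between interviews under the other.

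Logged counts are therefore likely to be incomplete, and not comparable between arms. How incomplete cannot be derived from the documents, and the zero-count probabilities above rest entirely on assumed inputs. The conclusion assumes that the unseen interview forms contain no side-effect or attempt item; if they do, the remedy reduces to describing them. The primary feasibility outcomes are not affected. The point limits what the safety counts can be used to say.

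**What to change.** First check the interview forms. Unless they already do this:

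1. Add one fixed side-effect item to the 1-, 3- and 6-month interviews in both arms, worded about any medicine so that it is identical for everyone. Ask it also at the 24-hour buprenorphine call that is already scheduled.
2. Add one item at each follow-up interview asking about overdose and suicide attempt 'since your last study interview'. After a missed interview, the look-back runs to the last completed one.
3. Enter the answers in the Anticipated AE/SAE log with their source.
4. Reconcile the two follow-up wordings of item 9a in Appendix C. Its clinical role is outside this point and is left unchanged.
5. State that any between-arm comparison uses only the common interview items and EDIE. Events found through care management, the study phone or the 24-hour call are listed but not compared.

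The SAP, dated September 2021, describes parts of the trial in the past tense. If data collection is over, replace the claim of systematic tracking with a statement that events were logged when the team became aware of them. Report the counts as passively ascertained, do not compare arms, and do not read low counts as tolerability.

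The cost is two short items and a minor amendment, or a change of wording only. The downside is a slightly longer interview, up to three months of recall at the last visit, and more recorded events, so the safety figures will look less favourable.
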